Poor oral health is common in frail and care-dependent older adults and includes tooth loss, poor oral hygiene, high prevalence of dental caries and periodontal disease, defective dental prostheses, hyposalivation and various oral lesions caused by misfitting dentures and/or precancerous or cancerous states [1,2]. Alarming, oral health is shown to be the most neglected area in Norwegian nursing homes [3] and oral healthcare is the first task to be downgraded due to lack of resources [4]. A study by Willumsen et al. [5] indicated that more than 40% of Norwegian nursing home residents have unacceptable oral hygiene. Neglect of oral health, resulting in poor oral hygiene, may cause infections and inflammation both locally and systemically. Oral infections have been associated with systemic conditions such as atherosclerosis [6,7], diabetes [8] and aspiration pneumonia [9,10]. Aspiration pneumonia is a highly mortal disease, and a review by Sjøgren et al. [11] estimated that 10% of all deaths from pneumonia in nursing homes could have been prevented with improved oral hygiene. Moreover, chewing difficulties as a result of poor dental status have been associated with altered dietary habits, malnutrition and cognitive decline [2]. Yet, the oral health of care-dependent elderly does not receive the necessary attention [12]. A few decades ago, most older adults were denture wearers. Today, an increasing number of elderly keep their natural teeth – often in combination with complex fixed and/or removable prosthesis [13]. While dentures are easy to manage, the more complex prosthetic devices can represent a challenge with regard to handling and cleaning [14]. Thus, care-dependent elderly have to rely on caregivers to maintain satisfactory oral health [15]. In Norway, nursing home residents (and other care-dependent people) have a statutory right to good oral hygiene and necessary dental treatment [16]. Health personnel are responsible for preserving these rights through daily oral hygiene routines and referral to dental professionals when needed. Research from Sweden and Denmark has shown that about 80% of nursing home residents need assistance with daily oral hygiene practices [15,17]. Thus, it is disturbing that healthcare professionals report numerous barriers when it comes to provision of adequate oral care assistance. The most frequently reported barriers are lack of knowledge and skills [18] and care resistant behaviors (CRB), in particular among patients suffering from dementia [18,19]. A study by Willumsen et al. [5] showed that more than 50% of Norwegian nursing home residents with dementia refuse oral care assistance. In cases of frequent CRB, daily oral care may be postponed repeatedly, resulting in poor oral hygiene and increased risk of oral and systemic infections. Other reported barriers include lack of adequate oral care routines, lack of systems for documentation of issues related to oral health [20,21], a high workload and unclear responsibilities [19].

Various tools have been developed to assist health personnel in providing oral care in frail elderly. One example is ‘oral care cards’ with illustrated instructions about how to carry out daily oral hygiene routines in individual patients. Another example is ‘signature lists’ to document daily oral care. These tools may function well but have some shortcomings. While oral care cards do not allow for documentation of oral health issues, signature lists do not contain information on individual needs. Moreover, text-based diagnostic tools such as the Revised Oral Assessment Guide (ROAG) [22] and the Oral Health Assessment Tool (OHAT) [23], have been developed to assist caregivers in recognizing oral conditions. However, research indicates that these tools may not be well suited for non-dental professionals [24,25].

Other limitations of the above-mentioned tools are that they lack procedures for documentation of deviance related to oral health, and that none of them include strategies for handling CRB.

1.1. SmartJournal

As a response to the shortcomings of existing tools, and to overcome reported barriers for provision of adequate oral care in nursing homes, an intervention tailored at nursing staff has been developed by researchers at the Oral Health Centre of Expertise in Rogaland, Norway, in close collaboration with innovative research- and development institutions, dental- and healthcare professionals. The intervention addresses key behavioural components as postulated by the capability, opportunity, motivation model of behaviour (COM-B model) [26]. According to the COM-B model, there must be sufficient capability (C), opportunity (O), and motivation (M) present for a given behaviour to occur. Hence, this intervention aims to facilitate oral care in nursing homes by providing strategies to improve caregivers' capability, opportunity and motivation for this task. The intervention is constructed as an interactive and easy-to-use mobile application for tablet named SmartJournal. SmartJournal consists of three modules: Module 1, 'registration of oral hygiene routines', offers a system for simple checkbox registration of daily oral hygiene routines (i.e., whether they have been performed or not). It also includes an open text field for additional comments if relevant (e.g., reasons for not performing oral hygiene routines and/or strategies used to reduce CRB in the patient). This straight-forward registration ensures documentation of oral hygiene routines and deviations related to such routines, keeping health personnel informed about potential oral hygiene issues for individual patients. Module 2, 'monthly oral health assessment', offers a system for monitoring the patient's oral health status through monthly check-ups. In this component, the principles of the text-based tool ROAG is transformed into an image-based, interactive learning- and assessment tool. As for ROAG, conditions for six oral sites (lips, mucous membranes, tongue, gingiva, teeth and prosthetic devices¹) are graded as follows: grade 1=healthy/normal condition, no need for measures; grade 2=pathology, need for measures at a 'local level' (i.e., at the nursing home, delivered by nursing home personnel); grade 3=advanced pathology, need for measures delivered by dental professionals (in the nursing home if feasible, at a dental clinic if necessary). SmartJournal contains several validated example pictures for each grade for all six oral sites. This part of the tool is also checkbox-based to limit health personnel's workload related to documentation. Upon completion of the monthly oral health assessment, health personnel receive a summary report with suggestions for tailored preventive and/or curative measures to be initiated, thus reducing the risk of deteriorated oral health in the patients. Module 3, 'e-learning', offers an easily accessible knowledge base which includes information on geriatric oral health, standard equipment and procedures for daily oral hygiene routines in patients with natural teeth and various prosthetic devices, and oral care for patients with special care needs (including patients with swallowing difficulties, bedridden patients and palliative care patients). It also includes detailed information on scientifically documented strategies that may be used to approach patients with dementia refusing oral care assistance. These strategies are adapted

¹ Prosthetic devices include all forms of removable dentures and fixed prosthodontics.

from the interventions ‘Managing Oral Hygiene Using Threat Reduction’ (‘MOUTH’) [27,28] and ‘Mouth Care Without a Battle’ (MCWB) [29]. The content in this part of the tool is illustrated with photos and figures and includes a video with recommendations on how to handle situations where patients refuse oral care assistance. Acceptability of the SmartJournal prototype has been tested in a feasibility study which has already been notified to, and approved by, the Regional Committee for Medical and Health Research Ethics (REK 2020/31294) and the Norwegian Centre for Research Data (NSD). Preliminary results from this study indicates that SmartJournal is well accepted among its users: According to survey data collected from caregivers employed at three nursing homes in Rogaland, Norway (n=86), 72% reported that SmartJournal is a useful tool, 94% reported that it is easy to use and 69% reported that they would like to use a refined version of the tool in the future.

2. Study objectives

Since SmartJournal seems to be well accepted among its potential users, the present study aims to evaluate *effects* of its usage. Thus, the objectives of the current research are to assess 1) the effectiveness of SmartJournal in enhancing nursing home caregivers' capability, opportunity, motivation and routines related to oral care tasks, 2) whether SmartJournal usage may result in improved oral health for nursing home residents and 3) whether SmartJournal usage may result in changes in the documentation of oral health related issues in patient journals.

3. Methods

3.1. Further improvement of the SmartJournal tool

Recently, SmartJournal has been further improved and adapted to the nursing home setting. Since user involvement is a central feature in the development of interventions [33], this improvement was guided by results obtained from the feasibility study (i.e., data acquired from meetings, qualitative interviews and survey questionnaires). Following this, the improved version was subjected to two functionality tests in a controlled laboratory environment. These tests were performed by Norwegian Smart Care Cluster (NSCC)². Insights gained through the functionality tests have been used for additional, minor adjustments of the tool, which is now ready to be tested in the evaluation study described in this protocol.

3.2 Design and recruitment

A pragmatic cluster randomized controlled trial (C-RCT) [34] will be employed to assess effects of SmartJournal usage as specified under study objectives. Public nursing homes located in the southern part of Rogaland county, Norway, will be recruited and randomly assigned to an intervention group and a control group. Institutions housing long-term residents will be included, while institutions with primarily short-term residents, institutions already following a specific protocol for oral care and/or participate in other comprehensive interventions are excluded. Nursing homes in the intervention group will be provided with

² NSCC: National and international collaboration arena for large and small companies, municipalities, hospitals, public organizations, user organizations, academia / R&D institutions and investors. The cluster works to develop sustainable health solutions for the future (<https://www.smartcarecluster.no/english/about-us>).

tablets containing SmartJournal, while nursing homes in the control group will continue with existing oral care routines. The intervention will last for 12 weeks. Measurements will be performed at baseline, 3 months and 9 months.

Strategies used for recruitment of individual participants (caregivers and residents), and procedures for delivery of the intervention, will be similar to those used in the feasibility study since they proved to be successful: resource groups, comprised of heads of wards and selected health personnel, will be established at each of the included nursing homes. Meetings will be scheduled to adapt delivery of the project to each individual institutions' resources and facilities, and members of the resource groups will be assigned the task of recruiting individual participants. Written informed consent will be requested for both residents and caregivers to be enrolled in the study. Nursing home residents constitutes a vulnerable group in which many individuals may have reduced decision-making capacity. For these individuals, deputy consent will be obtained from their next of kin. Residents receiving end-of-life palliative care are excluded. Both full- and parttime nursing staff will be included. Health personnel with purely administrative tasks (i.e., heads of institutions) are excluded. Following recruitment of participants and baseline measurements, nursing homes in the intervention group will be provided with SmartJournal toolboxes and packages with oral hygiene equipment, while nursing homes in the control group will receive oral hygiene equipment packages only. The SmartJournal toolboxes include tablets with SmartJournal installed, antibacterial touchscreen wipes, flashlights for monthly oral inspections, an instruction video, an instruction book and SmartJournal information posters. The oral hygiene equipment packages include toothbrushes for permanent teeth and prosthetic devices, dental floss, interdental brushes, toothpaste and inspection mirrors. Training, follow-up and technical support for SmartJournal users will be provided by project staff employed at the Oral Health Centre of Expertise Rogaland.

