3.4 Power calculations and estimation of sample size for clinical outcomes

Experiences from the feasibility study show that resident participation may comprise a challenge due to high rates of morbidity, mortality and CRB in this part of the population. Estimation of sample size is largely reproduced from Overgaard et al. [32] who also used MPS as a primary outcome variable in their study on oral health in nursing home residents. Overgaard et al. based their power calculations on reductions in $MPS \geq 2$ from 60% to 15% as reported by Hede et al. [17]. Like Overgaard et al. we assume an alpha of 0.5, a power of 80% and a 33% drop-out rate due to the residents' frail condition and a median resident time of two years. Using the programme G*Power 3 [35] for power calculations, Overgaard et al. found that at least 92 residents should be included in each group for oral health assessments. A medical statistician has been consulted to further adapt the calculations to the present study setting (taking into account the number of eligible nursing homes and residents in the southern part of Rogaland), recommending the inclusion of 12 nursing homes each with 30 residents opted for oral health assessments. Thus, a total of 360 residents will be included for oral health assessments, 180 in the intervention and control group, respectively. All eligible caregivers in the 12 included nursing homes will be invited to take part in the survey capturing components of the COM-B model as described in the Measurements section (4.2). Experiences from the feasibility study indicate that this broad inclusion strategy, along with assigning the recruitment task to members of the institutions' resource groups, foster a sense of community regarding project participation. This may, in turn, motivate institutions and individual participants to remain part of the project throughout the study period.

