Collaborating partners from academic institutions: *[name]* is professor at Department of Clinical Dentistry, University of Bergen. [name] will assist in statistical analyses and supervise [name]'s PhD work together with [name] and [name]. *[name]* is professor and vice dean for education at the Faculty of health, University of Stavanger. [name] was involved in early phases of the SmartJournal project and will be engaged in future usage of SmartJournal components in health education. *[name]* is professor at the Faculty of health and sport sciences, University of Agder. [name] is experienced in intervention research and will assist in quality control of the intervention, analyses and dissemination.

Other collaborating partners include: NETTOP-UiS, Centre for development of institutional and home care services (USHT) in Rogaland and Norwegian Smart Care Cluster (NSCC). Additional research environments and collaborators may be included at a later stage if feasible.

8. Funding

The initial phases of the SmartJournal project (i.e., development of the prototype and the feasibility study) were funded by the Norwegian Regional Research Funds Vestland (RFF Vestland) and the Oral Health Centre of Expertise - Rogaland (TkRog) (project ID: 291051/2018). The research described in this protocol (i.e., the evaluation study) has recently received funding from the Norwegian Regional Research Funds Rogaland (RFF Rogaland, project ID: 332666/2022).

9. Time schedule

The study is scheduled between 01.02.2023 and 31.12.2025 (Table 1).

Table 1. Anticipated time schedule and research activities.

Activities	From	Quarter	To	Quarter
Recruitment and baseline measurements (T0)	2023	1	2023	2
Intervention*	2023	3	2023	4
Measurements at 3 months (T1)*	2023	4	2024	1
Measurements at 9 months (T2)*	2024	1	2024	3
Analyses and dissemination	2024	4	2025	4

*The intervention will last for 12 weeks. Since the start date may vary between included nursing homes, a 12 month period is scheduled to perform the intervention and measurements at T0, T1 and T2.

10. References

2. Kossioni A. The association of poor oral health parameters with malnutrition in older adults: a review considering the potential implications for cognitive impairment. *Nutrients*. 2018;10(11):1709.

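### Ward staff of the randomised homes recruit the residents with no selection rule, and the protocol does not place allocation or its disclosure after recruitment and baseline

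*Protocol*

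**What the plan says.** Section 3.2 of the protocol describes a cluster design in which public nursing homes "will be recruited and randomly assigned to an intervention group and a control group". It then explains how individuals enter the trial:

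- In every home, "resource groups, comprised of heads of wards and selected health personnel, will be established at each of the included nursing homes".
- One sentence then covers both the planning meetings, which fit the project to each home's circumstances, and the recruiting task: "members of the resource groups will be assigned the task of recruiting individual participants".
- The one step with a stated position in time is the hand-over of equipment: "Following recruitment of participants and baseline measurements, nursing homes in the intervention group will be provided with SmartJournal toolboxes". Control homes receive hygiene packages only.

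Section 3.4 reports the statistician's advice as "12 nursing homes each with 30 residents opted for oral health assessments". The only exclusion of residents in 3.2 is end-of-life palliative care. All eligible caregivers in the 12 homes are to be invited to the survey (3.4).

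Table 1 in section 9 has one row for recruitment and baseline (2023, quarters 1 to 2) and one for the intervention (quarters 3 to 4). It has no row for randomisation. Nowhere does the protocol say when homes are allocated relative to the consent of residents, or that allocation is withheld from the resource groups until recruitment is complete.

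**The concern.** In a cluster trial, randomising homes makes the homes comparable. It makes the enrolled residents comparable only if they are identified and consented without knowledge of the arm. Here the recruiters are the staff whose wards will or will not use the app on the people they enrol.

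The recruiters also have room to choose, because there is a target of 30, almost no exclusion and no approach rule. The trait most likely to guide them is both common and relevant to the outcome. Section 3.4 names care-resistant behaviour as an obstacle to resident participation, and section 1 links it to poor oral hygiene and says that more than half of residents with dementia refuse oral care assistance.

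The recruitment method is carried over from the feasibility study, which section 1.1 describes as a test of acceptability. Section 3.4 defends staff-led recruitment by its effect on community and retention. Neither reason bears on whether two arms stay comparable. At stake is the primary resident comparison at 3 and 9 months and, through willingness to consent, the caregiver survey.

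**Working it through.** **1. The order of events.** Setting the passages side by side:

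| Step | Position given in the protocol |
|---|---|
| Homes recruited and randomised | Described first in 3.2; not placed relative to resident recruitment |
| Resource groups and meetings | At every included home; not placed relative to allocation |
| Residents and caregivers recruited by resource-group members | Before toolboxes; not placed relative to allocation |
| Baseline measurements | Before toolboxes |
| Toolboxes and hygiene packages delivered | After recruitment and baseline |
| Disclosure of allocation | Not mentioned |

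The text is compatible with allocation before or after consent, and a home following it as written could recruit with its arm known.

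**2. Sample size.** 12 × 30 = 360, or 180 per arm, agrees with section 3.4. No stated figure is in dispute.

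**3. Size of a possible bias at follow-up, baseline ignored.** All inputs are assumptions, chosen so that the control arm matches the figure of more than 40% unacceptable hygiene in section 1. Assume poor hygiene in 60% of care-resistant residents and 20% of others, and no effect of SmartJournal. Suppose 50% of enrolled control residents and 35% of enrolled SmartJournal residents are care-resistant.

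- Control: 0.50 × 0.60 + 0.50 × 0.20 = 0.40
- SmartJournal: 0.35 × 0.60 + 0.65 × 0.20 = 0.34
- Spurious difference: 0.15 × (0.60 − 0.20) = 0.06

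In general the difference is the selection gap × 0.40: a gap of 5 points gives 0.05 × 0.40 = 0.02, and one of 25 points gives 0.25 × 0.40 = 0.10. If the gap runs the other way, the sign reverses.

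**4. Effect on the error rate, again unadjusted.** A second set of assumptions matches the 60% starting level used in section 3.4: poor MPS in 75% of hard-to-treat residents and 45% of others, and 33% drop-out, leaving 180 × 0.67 = 120.6 per arm. With 60% of control and 40% of SmartJournal residents hard to treat (a gap of 20 points):

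- Control: 0.60 × 0.75 + 0.40 × 0.45 = 0.63
- SmartJournal: 0.40 × 0.75 + 0.60 × 0.45 = 0.57

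The chance of a significant result in that direction is about 16% with an intracluster correlation (ICC) of 0, and about 10% with an ICC of 0.05, against a nominal 2.5%. Gaps of 10 and 30 points give about 7% and 30% (ICC 0), or 5% and 17% (ICC 0.05).

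**5. What baseline does to this.** In step 3, if the resident mix is fixed and nothing else changes, baseline is also 40% against 34%. The difference in change is (0.34 − 0.34) − (0.40 − 0.40) = 0. A bias remains if care-resistant residents change differently over time from others. With a selection gap d and changes gR (resistant) and gO (others), the difference in change is −d × (gR − gO), which is zero only if the two groups move in parallel. Different drop-out in the two groups can add to it. The covariates listed in 3.3 are socio-demographics, medical conditions and medication; care-resistant behaviour is not among them. Section 3.5 makes covariate-adjusted regression optional.

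**The case against.** The strongest reply is that the protocol does not say recruiters know their arm. A reader might infer from the order of sentences in 3.2 that they do, or that meetings to adapt delivery presuppose it. The documents do not support either inference. The sentence on random assignment is a summary of the design. The meetings concern the project at every included home, control homes among them, and consent, MPS visits, surveys and journal extraction all need planning whatever the arm. Table 1 leaves room for allocation after baseline, and a missing randomisation row proves nothing about order. This stands: unblinded recruitment is a possibility left open, not a stated procedure.

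Four further points stand in part:

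- **Direction.** Leaving out resistant residents would flatter SmartJournal; seeking out those thought likely to benefit could bring in worse mouths and do the reverse. Control staff too may avoid resistant residents, since MPS examinations take place in both arms.
- **Baseline.** MPS is measured at baseline and section 3.5 looks at change, so the 2 to 10 points are not the expected bias of a baseline-adjusted analysis.
- **Room for choice.** This depends on how many residents are eligible per home, which is not given. If that is close to 30, there is little choice.
- **Scale.** Six points is small beside the planned reduction from 60% to 15%.

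None of this closes the gap. Who enrols residents, and whether the arm is known at that time, is a matter of conduct that later analysis cannot fully undo.

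**Conclusion.** The point holds as a weakness of the recruitment design: the homes' own staff recruit, no rule governs which 30 residents are approached, and nothing keeps allocation from the recruiters until consent and baseline are complete. It would be too strong to say that recruiters are unblinded or that the result will favour SmartJournal; the protocol supports only that differential selection is not prevented, and its direction is uncertain.

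The illustrated size, 2 to 10 points of spurious difference for selection gaps of 5 to 25 points, rests wholly on assumed values and on a follow-up comparison unadjusted for baseline. Baseline adjustment would shrink it, to zero if resistant and other residents change in parallel, but that cannot be relied on. For caregivers there is no selection by recruiters in whom to invite, only possible differential consent. Confidence is moderate; the change is worth making because it is cheap and the problem cannot be repaired after enrolment.

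**What to change.** In section 3.2, fix the order for each home:

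1. The home agrees to take part.
2. Residents are approached in random or consecutive order from the home's list of eligible residents until 30 consent; all eligible caregivers are invited and their consent is completed.
3. All baseline measurements are completed: MPS, survey and journal extraction.
4. Only then is that home's allocation disclosed, from a list prepared beforehand and not held by the home or the recruiters.
5. Arm-specific planning of delivery and training follows disclosure. No one enrolled after disclosure enters the analysed cohort.

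Resource groups can still do the recruiting, and general planning meetings can still come before it. The sequence fits the existing rule that toolboxes follow baseline. If allocation after baseline is already intended, one sentence settles the timing, but the approach order still has to be stated.

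The cost is protocol wording and scheduling, an eligibility list per home, and someone to hold the allocation list. No extra participants are needed. The small downside is that homes consent without knowing their arm, and training can be scheduled only after that home's baseline.
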